14.7 Early Discontinuation

If the subject is withdrawn from the study before completion of the study, the reason for withdrawal from the study must be documented in the subject's source document and eCRF. Whenever a subject withdraws, the procedures/assessments listed below should be conducted.

- Evaluation of adverse events;
- Complete physical exam (including vital signs and weight);
- FVC (as clinically warranted);
- Clinical laboratory tests (fasting), including full chemistry panel (including glucose and alkaline phosphatase), hematology, and urinalysis;
- Urine pregnancy test;
- Neurologic exam;
- Dental exam by a licensed dentist (including 4 bite-wing radiographs or panoramic imaging [if edentulous or if bite-wing x-rays are difficult due to limited teeth]);
- C-SSRS Since Last Visit version;
- Review of concomitant medications;
- Review of subject diary;
- CGI-S and CGI-C (Assessor) before USFR;
- USFR collection;
- DFSS-I;
- PGI-S and PGI-C (Subject);
- DIS (Subject); and
- DFSS-S via entry in subject's diary, not during study visit.

14.8 Interim Telephone Follow-ups

Study staff will perform an Interim Telephone Follow-Up 24 hours (± 1 day) after the first injection of MYOBLOC, 1 week (± 1 day) after each subsequent injection of MYOBLOC, and at Weeks 21, 34, and 47 (± 5 days) to assess how the subject feels, document adverse events as appropriate, review concomitant medications, and to remind the subject to complete their diary.

14.9 Post-Study Telephone Contact

If a subject discontinues study participation because of an adverse event, the subject will be evaluated in the office as soon as possible, and also contacted 13 weeks (± 3 days) after the last injection of study drug to determine if the adverse event has resolved, continues unabated, or has reached a new baseline.

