16.2 Adverse Events

All adverse events and details for the events will be recorded on the subject's source document and on the Adverse Event eCRF. An adverse event should be documented in terms of a medical diagnosis. When this is not possible, the adverse event should be documented in terms of signs and/or symptoms observed or reported.

Adverse events can be collected by either the Investigator or the Study Coordinator; however, the Investigator must determine the intensity of the adverse event (Section 16.2.2.1), assess whether or not the study drug caused the adverse event (Section 16.2.2.2), record whether the adverse event led to discontinuation of the subject from the study (Section 16.2.2.3), record the outcome of the adverse event (Section 16.2.2.4), and determine if the adverse event is serious (Sections 16.2.2.5 and 16.2.6).

For this study, adverse events will be collected beginning with the start of dosing on Day 1 and will end at study completion (52 weeks \pm 1 week). Subjects who discontinue because of an adverse event before study completion will be contacted 13 weeks (\pm 3 days) after their last injection of study drug (see Section 16.2.7). Serious adverse events will be collected after signing informed consent until 30 days after study completion if the study site becomes aware of the event.

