16.2.8 Adverse Event Reporting

16.2.8.1 Adverse Events Requiring Expedited Reporting

The following events should be forwarded to the Sponsor within 24 hours of becoming aware of the event:

- All SAEs, regardless of causality;
- Overdose (with or without an adverse event);
- Inadvertent or accidental exposure;
- All adverse events of special interest (see Section 16.2.4);
- Pregnancy (see Section 16.2.5); and
- Unexpected therapeutic benefit.

16.2.8.2 Timeframe for Collecting and Reporting Serious Adverse Events, Adverse Events of Special Interest, and Other Immediately Reportable Adverse Events

Serious adverse events, adverse events of special interest, and other immediately reportable adverse events occurring during the study period (or within 13 weeks ± 3 days of last study drug injection for subjects discontinuing participation prematurely) must be reported via telephone to the Medical Monitor or designee and then followed up using the appropriate Adverse Event Form, **within 24 hours** of the time any study staff member is made aware of the event. Additional eCRF and/or paper documentation may need to be supplied to the Sponsor (or designee).

You must also report any SAE of which you become aware that occurred within 13 weeks after the last dose of study drug (regardless of relationship to study drug). Any SAEs (at least possibly related to study drug) that you become aware of after 13 weeks after the last dose of study drug should also be reported to the Sponsor (or designee). These post-study events should be reported to the Sponsor using MedWatch Forms

When reporting adverse events of special interest, study staff should provide copies of supporting documentation described in Section 16.2.4. Please note that the supporting documentation provided must be redacted to remove any subject identifiers other than the study subject identification number and subject's initials.

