19.4 Adverse Event Reporting

In accordance with FDA reporting requirements, you are required to collect, document, and report all adverse events/SAEs as outlined in Section 16.2.8 of this protocol. You must also report any SAE of which you become aware that occurred within 13 weeks after the last dose of study drug (regardless of relationship to study drug) and any SAEs (at least possibly related to study drug) that you become aware of after 13 weeks after the last dose.

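### The SAE and AESI end date for early leavers is not consistent, and the only planned contact at 13 weeks is for those who left because of an adverse event

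*Protocol*

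**What the plan says.** **Reporting window.** Protocol 16.2.8.2 requires SAEs, AESIs and other immediately reportable events to be reported during the study, or within 13 weeks ± 3 days "of last study drug injection for subjects discontinuing participation prematurely". The reason for leaving does not matter. SAP 2.6.2 repeats this window. The next paragraph of 16.2.8.2 adds: "You must also report any SAE of which you become aware that occurred within 13 weeks after the last dose of study drug", whatever the causality. SAEs at least possibly related "that you become aware of after 13 weeks after the last dose of study drug should also be reported", with no end date. Protocol 19.4 restates both duties.

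**Collection window.** Protocol 16.2 says that "adverse events will be collected beginning with the start of dosing on Day 1 and will end at study completion", given there as 52 weeks ± 1 week. SAEs are collected from consent "until 30 days after study completion if the study site becomes aware of the event".

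**Planned contact.** Protocol 14.9 provides a contact at 13 weeks (± 3 days) after the last injection under one condition: "If a subject discontinues study participation because of an adverse event". Protocol 16.2, 16.2.7, footnote (f) of the second part of Table 2, and SAP 2.6.2 carry the same restriction. In 14.9 and 16.2.7 the stated purpose is to learn whether the known event has resolved, is continuing or has settled at a new level.

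**Exit visit.** Protocol 12.3 and 14.7 ask every leaver for early discontinuation assessments, including an adverse event evaluation. Nothing ties that visit to 13 weeks after injection.

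**The concern.** Long-term safety is the primary objective, and the AESIs (aspiration, aspiration pneumonia, choking, dysphagia) are named safety endpoints. The reportable period is set at 13 weeks for all early leavers, but most reasons for leaving have no step that would find an event late in that period. Protocol 12.3 itself creates early exits that are not AE-related: lack of effectiveness is judged at Week 4.

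Sites could also apply different end dates to the same subject, depending on whether they follow 16.2 or 16.2.8.2. Non-serious AESIs, such as mild dysphagia, are the most exposed. The 30-day extension in 16.2 and the additional 13-week duty in 16.2.8.2 and 19.4 are written for SAEs only.

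The SAP reports the number and proportion of subjects with events by session. An early leaver counts in the session already started, so events not found after exit would lower the reported proportion.

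**Working it through.** The plan states no figure on this point, so there is none to reproduce. The check is calendar arithmetic.

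**Inputs.** The 13-week limit (16.2.8.2, SAP 2.6.2); 30 days = 30/7 = 4.29 weeks (16.2); last injection at Week 39 and final visit at Week 52 ± 2 weeks (Table 2). Let t be the weeks from last injection to exit.

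**Completers.** 30 days after completion is 13 + 4.29 = 17.3 weeks after the last injection (15.3 to 19.3 with the ± 2 week visit window). This is longer than 13 weeks, so completers have no shortfall.

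**Early leavers: what is study completion?** Section 12.3 classes anyone who does not complete as a premature termination, so an early leaver has no completion date of their own. Two readings are possible.

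- *Own exit.* SAE collection ends at t + 4.29 weeks. The shortfall against 13 weeks is max(0, 13 − 4.29 − t) = max(0, 8.71 − t). AE collection, and with it collection of non-serious AESIs, ends at t.
- *Week 52.* SAE collection ends at 52 + 4.29 = 56.3 weeks from Day 1. The latest nominal 13-week limit is 39 + 13 = 52 weeks, so there is no shortfall.

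**Time without planned contact** for a leaver whose exit was not AE-related: 13 − t weeks.

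| Exit, weeks after last injection | SAE collection ends (own-exit reading) | Shortfall against 13 weeks | Weeks without planned contact |
|---|---|---|---|
| 1 | 5.3 | 7.7 | 12 |
| 4 | 8.3 | 4.7 (4.3 to 5.1 with ± 3 days) | 9 |
| 8 | 12.3 | 0.7 | 5 |
| 13, not reinjected | 17.3 | 0 | 0 |

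On the own-exit reading the SAE shortfall vanishes for exits at or after about 8.7 weeks. The last column does not depend on which reading is taken.

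**Number affected.** No dropout rate is given. As an illustration only, take the 187 subjects of SAP 2.5 and assume that 5% to 20% leave for reasons other than an AE:

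- all exit at Week 4: 187 × 0.05 × 9 = 84 to 187 × 0.20 × 9 = 337 person-weeks without planned contact;
- all exit at Week 8: 187 × 0.05 × 5 = 47 to 187 × 0.20 × 5 = 187 person-weeks;
- all exit at Week 13 without reinjection: 0.

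The range is too wide to serve as an estimate.

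**The case against.** The strongest reply is that nothing here is a true contradiction. A site that applies the longest window satisfies 16.2, 16.2.8.2 and 19.4 together. SAEs that it learns of within 13 weeks must be reported whatever the reason for leaving. Leavers are not abandoned: all are asked for an exit evaluation, those leaving for lack or loss of effectiveness are encouraged to return, non-returners get repeated contact attempts, known events are followed to resolution or stabilization, and pregnancies are followed to their end. Whether to call other leavers is then a design choice.

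Much of this stands, and it rules out several stronger readings that a reader might infer:

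- *That SAE collection stops short of 13 weeks.* The 30 days run from study completion, not from the last injection. The window is short only for early leavers, only on the own-exit reading, and only for exits before about 8.7 weeks.
- *That late events are missed.* Passive reporting still applies. The text supports only that they may be under-ascertained.
- *That 14.9 conflicts with the reporting window.* It follows up a known event and is not a collection rule.
- *That AE-related leavers are fully ascertained and the others are not.* The call has no stated question about new events, so the text does not establish a clean contrast by reason for leaving.
- *That the SAP discards late events.* SAP 2.9.2 sets no upper cut-off for treatment-emergent events, so whatever is collected is tabulated. SAP 2.6.2 omits the 30-day rule, but it describes collection, not analysis.

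The reply does not supply a defined end date for early leavers, or any planned step that would find a new SAE or AESI after the exit visit.

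**Conclusion.** The point holds as an inconsistency and an ascertainment gap of limited size. The documents give early leavers a 13-week reportable period in one place and an end date with an undefined anchor in another; the two readings of that anchor fall on opposite sides of 13 weeks for early exits. After the exit visit, capture of new SAEs and AESIs in leavers whose exit was not AE-related is passive, apart from pregnancy follow-up. Any resulting bias in the counts is likely to be downward.

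The size per subject is 9 weeks without planned contact for a Week 4 exit, 5 for Week 8 and none for Week 13 without reinjection. These figures assume nominal visit timing and an exit visit held at the time of leaving. The total effect is unknown without a dropout rate and the timing of exits. This is a cheap improvement to safety ascertainment; it does not show that the trial's safety results are wrong.

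**What to change.** 1. Reconcile Protocol 16.2, 16.2.8.2 and 19.4 and SAP 2.6.2 to one SAE and AESI end date for every subject: the later of 30 days after the last visit and 13 weeks after the last injection. Anchoring to the subject's own last visit and last injection removes the undefined term.
2. Extend the 13-week call in 14.9, with the matching text in 16.2, 16.2.7, Table 2 footnote (f) and SAP 2.6.2, to all early leavers who agree to contact. State that it asks about new SAEs and AESIs as well as known events. Widening the call without changing its content would not close the gap.
3. If follow-up is already closed, which the past-tense wording in parts of the SAP suggests, have the SAP state the window applied and disclose that capture after exit was passive in leavers whose exit was not AE-related.

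The cost is wording in two documents and one call per such leaver by existing site staff. Subjects who refuse contact or are lost to follow-up remain uncovered.

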15 EFFECTIVENESS ASSESSMENTS

Global Measures of Effectiveness

The global measures of effectiveness by the clinician (CGI-S and CGI-C) should be completed before the quantitative measure of saliva.

Assessors

In order to maintain consistency of rating assessments, an assessor will be trained (i.e., Investigator or other clinician named on Form FDA 1572) and this same assessor should perform a given assessment for a subject throughout the study. Another assessor (clinician named on Form FDA 1572) will also undergo training to ensure consistency in scale ratings should a back-up assessor be necessary to perform assessment(s).

Caregiver Assistance

If a subject elects to have a caregiver assist with completing rating scale activities, that same caregiver should then consistently assist with the ratings throughout the study. Note that the caregiver may assist in the physical completion of scales, but all responses recorded on the scales must be provided from the subject either verbally or by gesture.

Study Participants with Parkinson's Disease

Therefore, PD subjects should complete the rating scales at least 1 hour after their first dose of PD medication and at least 1 hour postprandial.

Study Participants with ALS

For ALS subjects on short-acting anticholinergics or antihistamines (duration of action of 8 hours or less), for the treatment of troublesome sialorrhea, these medications must be held at least 8 hours before the screening, baseline, and all subsequent study visits, so that the effectiveness of the study drug can be properly evaluated. All subjects must be converted to a short-acting medication (duration of action of approximately 8 hours or less) at least 2 weeks before the first injection of study drug (i.e., Day 1 of Treatment Session 1).

15.1 Unstimulated Salivary Flow Rate (USFR)

Salivary flow rate, as described by Proulx and colleagues [2005] and Vivino and colleagues [1999] will be determined in an unstimulated state (i.e., at least 1 hour postprandial) at screening, just before the first injection of study drug (Day 1) to establish a baseline salivary flow rate, and at each subsequent study visit according to instructions detailed in Appendix B. Briefly, saliva will be collected over a 5-minute collection period using weighing cups

They will be asked to expectorate, as needed, any saliva that accumulates in their mouth into the pre-weighed cup during the 5-minute collection period.

Although not a rating scale, the same person should conduct this assessment throughout the study to minimize collection technique bias.

15.2 Clinical Global Impression of Severity (CGI-S) and Change (CGI-C)

The CGI-S scale will be used to record the severity of illness (sialorrhea) on Day 1 (i.e., study baseline) before the first injection of study drug, at each subsequent study visit or, if applicable, at discontinuation from the study. CGI-S will be assessed by a trained assessor on a 7-point scale ranging from “normal” to “among the most extremely ill patients” (Appendix C). The CGI-C, used to record change or improvement in illness from baseline (i.e., pre-injection) of each treatment session, will be assessed at each study visit after Day 1 by the assessor on a 7-point scale ranging from “very much improved” to “very much worse” (Appendix C). Both CGI scales will be completed independent of the subject’s self-assessment (PGI-S and PGI-C) so neither party knows how the other has rated the scales.

15.3 Patient Global Impression of Severity (PGI-S) and Change (PGI-C)

The PGI-S scale will be used by the subject to rate the severity of his/her illness (sialorrhea) on Day 1 (i.e., study baseline) before the first injection of study drug, at each subsequent study visit, or, if applicable, at discontinuation from the study. PGI-S will be assessed on a 8-point scale ranging from “normal” to “among the most extremely ill” (Appendix D). The PGI-C will be used by the subject to rate his/her impression of change in symptoms (drooling or sialorrhea) from Day 1 (i.e., study baseline) or just before subject’s most recent injection of study drug to the time of assessment at each study visit. The PGI-C is assessed on a

7-point scale ranging from “very much improved” to “very much worse” (Appendix D).

Both PGI scales need to be completed independent of the assessor who completes the CGI scales so neither party knows how the other has rated the scales.

15.4 Drooling Frequency and Severity Scale (DFSS)

The DFSS will be used to assess the frequency and severity of drooling. The DFSS-I will be performed by a trained assessor independent of the DFSS performed by the subject (DFSS-S) (Appendix E). The DFSS-I will be completed at screening, on Day 1 (i.e., study baseline) before the first injection of study drug, at each subsequent study visit, or, if applicable, at discontinuation from the study. Severity is assessed on a 5-point scale ranging from 1 (dry, never drools) to 5 (profuse, clothing, hands, tray, objects become wet). Frequency is assessed on a 4-point scale ranging from 1 (never drools) to 4 (constantly drools). The DFSS total score ranges from 2 to 9. The assessor’s initial assessment at screening should be based on the prior 4 weeks, with subsequent assessments based on the timeframe since the prior study visit. The assessor should not review the subject-rated scales before performing his/her own assessment. The subject will complete this assessment in the diary on a daily basis for the first 2 weeks of each treatment session and then weekly for the remainder of the treatment session.

15.5 Drooling Impact Score (DIS)

The DIS is a 10-item questionnaire with each item rated by the subject to evaluate the impact of sialorrhea on daily activities (e.g., speech, social activities) (Appendix F). The DIS will be completed on Day 1 (i.e., study baseline) before the first injection of study drug, at each subsequent study visit, or, if applicable, at discontinuation from the study. For each question the subject is requested to compare their current status to their last study visit using a 4-point scale ranging from 1 (not at all) to 4 (very much). The DIS total score ranges from 10 to 40. On Day 1 before the first injection of study drug, the subject will be asked to reference the prior 4 weeks, with subsequent assessments based on the timeframe since the prior study visit.

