Patient Global Impression of Severity (PGI-S) and Change (PGI-C)

The PGI-S scale will be used by the subject to rate the severity of his/her illness (sialorrhea) on Day 1 (i.e., study baseline) before the first injection of study drug, at each subsequent study visit, or, if applicable, at discontinuation from the study. PGI-S will be assessed on a 8-point scale ranging from “normal” to “among the most extremely ill” (Appendix D of the protocol). The PGI-C will be used by the subject to rate his/her impression of change in symptoms (drooling or sialorrhea) from Day 1 (i.e., study baseline) or just before subject’s most recent injection of study drug to the time of assessment at each study visit. The PGI-C is assessed on a 7-point scale ranging from “very much improved” to “very much worse” (Appendix D of the protocol). Both PGI scales need to be completed independent of the assessor who completes the CGI scales so neither party knows how the other has rated the scales.

Drooling Frequency and Severity Scale (DFSS)

The DFSS is a 2-item scale used to assess the frequency and severity of drooling. The DFSS will have two forms in this study, with one being performed by an independent assessor (DFSS-I) and the other by the subject (DFSS-S). In both forms, drooling severity is assessed on a 5-point scale ranging from 1 (dry, never drools) to 5 (profuse, clothing, hands, tray, objects become wet), whereas drooling frequency is assessed on a 4-point scale ranging from 1 (never drools) to 4 (constantly drools) (Appendix E of the protocol). The total score ranges from 2 to 9 in each DFSS form. The assessor’s initial assessment

of DFSS on Day 1 of Treatment Session 1 should be based on the prior 4 weeks, whereas the subsequent assessments of DFSS should be based on the timeframe since the prior study visit. The independent assessor should not review the subject-rated scales before performing his/her own assessment.

DFSS-S is collected via subject's diary in this study on a daily basis for the first 2 weeks of each treatment session and then weekly for the remainder of the treatment session.

Drooling Impact Score (DIS)

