The DIS is a 10-item questionnaire with each item rated by the subject to evaluate the impact of the disorder (sialorrhea) on daily activities (e.g., speech, social activities). For each question, the subject is requested to compare their current status to their last study visit using a 4-point scale ranging from 1 (not at all) to 4 (very much) (Appendix F of the protocol). The DIS total score ranges from 10 to 40. The initial assessment of DIS on Day 1 of Treatment Session 1 before the first injection of study drug should be based on the prior 4 weeks, whereas the subsequent assessments should be based on the timeframe since the prior study visit.

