4.4 Efficacy Results and Tabulations

Descriptive and inferential statistics of USFR (g/minute) and changes from pre-injection at Day 1 to Weeks 4, 8 and 13, for Treatment Session 1 and from each subsequent pre-injection at Weeks 13, 26 and 39 (Treatment Session 2, 3 and 4) to 4 and 13 weeks following it respectively, will be presented for the ITT population.

Descriptive and inferential statistics of DFSS-I and changes from pre-injection at Day 1 to Weeks 4, 8, and 13, for Treatment Session 1 and from each subsequent pre-injection at Weeks 13, 26 and 39 (Treatment Session 2, 3 and 4) to 4 and 13 weeks following it, respectively, will be presented for the ITT population.

Descriptive and inferential statistics of DFSS-S and changes from pre-injection at Day 1 to Weeks 4, 8, and 13, for Treatment Session 1 and from each subsequent pre-injection at Weeks 13, 26 and 39 (Treatment Session 2, 3 and 4) to 4 and 13 weeks following it, respectively, will be presented for the ITT population.

Descriptive and inferential statistics of CGI-S and changes from pre-injection at Day 1 to Weeks 4, 8, and 13, for Treatment Session 1 and from each subsequent pre-injection at Weeks 13, 26 and 39 (Treatment Session 2, 3 and 4) to 4 and 13 weeks following it, respectively, will be presented for the ITT population.

Descriptive and inferential statistics of CGI-C at pre-injection (except for Day 1), and at Weeks 4, 8, and 13 for Treatment Session 1 and from each subsequent pre-injection at Weeks 13, 26 and 39 (Treatment Session 2, 3 and 4) to 4 and 13 weeks following it, respectively, will be presented for the ITT population.

Descriptive and inferential statistics of the proportion of the CGI-C treatment responders with much improved or better at pre-injection (except for Day 1) and at Week 4, 8, 13 weeks post injection for Treatment Session 1 and from each subsequent pre-injection at Weeks 13, 26 and 39 (Treatment Session 2, 3 and 4) to 4 and 13 weeks following it, respectively, will be presented for the ITT population.

Descriptive and inferential statistics of PGI-S and changes from pre-injection at Day 1 to Weeks 4, 8, and 13, for Treatment Session 1 and from each subsequent pre-injection at Weeks 13, 26 and 39 (Treatment Session 2, 3 and 4) to 4 and 13 weeks following it, respectively, will be presented for the ITT population.

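### DFSS-I and DIS look back to the prior study visit, so the pre-injection baselines of Sessions 2–4 include treated weeks and the session-by-session changes are not like-for-like

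*Protocol*

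**What the plan says.** **Recall rule.** For DIS (Protocol 15.5), the Day 1 rating refers to the preceding 4 weeks, "with subsequent assessments based on the timeframe since the prior study visit". SAP 2.6.1 repeats this for DIS: "whereas the subsequent assessments should be based on the timeframe since the prior study visit". Protocol 15.4 applies the same rule to DFSS-I but places the 4-week period at screening: "initial assessment at screening should be based on the prior 4 weeks, with subsequent assessments based on the timeframe since the prior study visit". SAP 2.6.1 also has later DFSS ratings run from the prior visit, but it places the 4-week period elsewhere: the assessor's first rating "of DFSS on Day 1 of Treatment Session 1 should be based on the prior 4 weeks".

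**A second DIS reference.** Protocol 15.5 also states: "For each question the subject is requested to compare their current status to their last study visit". That asks about status now, not about a period.

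**Visits.** Protocol 10 schedules study visits at Weeks 4, 8, 13, 17, 26, 30, 39, 43 and 52. Only Session 1 has an 8-week clinic visit. In later sessions that contact is a telephone call, listed apart from the visits, with no DIS or DFSS-I scheduled.

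**Analysis.** SAP 2.9.1 takes Day 1 and Weeks 13, 26 and 39 as the baselines of Sessions 1 to 4. SAP 4.4 presents DFSS-I and DIS change from Day 1 to Weeks 4, 8 and 13, and then "from each subsequent pre-injection at Weeks 13, 26 and 39 (Treatment Session 2, 3 and 4) to 4 and 13 weeks following it". Neither document fixes a common recall length or adjusts for it.

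**The concern.** A change from pre-injection is meant to set a treated state against the state just before treatment. A rating that covers the whole interval since the last visit does not measure the state just before treatment. From Session 2 onward that interval lies after the previous injection, and its length depends on whether an 8-week clinic visit was held. Session 1 has an untreated baseline, Session 2 a baseline covering 5 post-injection weeks, and Sessions 3 and 4 baselines covering 9.

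The secondary objective is to assess the magnitude of response after repeated treatments. Session tables set side by side could show a shrinking 4-week change on these two scales even if every injection worked equally well.

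**Working it through.** The plan states no figure on this point, so there is none to reproduce.

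**Step 1. Nominal look-back** = week of visit − week of previous study visit (Protocol 10).

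| Visit (week) | 4 | 8 | 13 | 17 | 26 | 30 | 39 | 43 | 52 |
|---|---|---|---|---|---|---|---|---|---|
| Look-back (weeks) | 4 | 4 | 5 | 4 | 9 | 4 | 9 | 4 | 9 |

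**Step 2. With visit windows**, in days after the session's injection (end-of-session visit at 11–15 weeks, i.e. days 77–105).

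- Week 13, after a Week 8 visit at day 56 ± 3: (77 − 59)/7 = 2.6 to (105 − 53)/7 = 7.4 weeks.
- Weeks 26, 39 and 52, after a 4-week visit at day 28 ± 5: (77 − 33)/7 = 6.3 to (105 − 23)/7 = 11.7 weeks.

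**Step 3. Period behind each session baseline.** Session 1: before any study injection. Session 2: weeks 8–13 after injection 1. Session 3: weeks 4–13 after injection 2. Session 4: weeks 4–13 after injection 3.

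**Step 4. Illustrative size.** Assumptions, none of them from the documents:

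- raters average over the look-back;
- the true course is the same after every injection;
- benefit rises linearly from 0 to peak (= 1) over week 0–1 and is 0 at week 13.

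Three waning patterns are used: A, peak to week 4, then linear to 0 at week 13; B, peak to week 8, then linear to 0 at week 13; C, peak to week 4, then linear to 0 at week 8.

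Mean benefit by recall period:

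- Weeks 0–4, all curves: (0.5 + 3)/4 = 0.875.
- Weeks 8–13: A, 0.556/2 = 0.278; B, 0.500; C, 0.
- Weeks 4–13: A, 0.500; B, (4 + 2.5)/9 = 0.722; C, 2/9 = 0.222.

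Change at 4 weeks = 0.875 − baseline. Change at 13 weeks = end-of-session mean − baseline.

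| | Curve | Session 1 | Session 2 | Sessions 3 and 4 |
|---|---|---|---|---|
| Baseline carries | A | 0 | 0.28 | 0.50 |
| | B | 0 | 0.50 | 0.72 |
| | C | 0 | 0 | 0.22 |
| 4-week change | A | 0.87 | 0.60 | 0.37 |
| | B | 0.87 | 0.37 | 0.15 |
| | C | 0.87 | 0.87 | 0.65 |
| 13-week change | A | 0.28 | 0.22 | 0 |
| | B | 0.50 | 0.22 | 0 |
| | C | 0 | 0.22 | 0 |

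**Step 5. Same model, change from Day 1.** The look-backs at Weeks 4, 17, 30 and 43 all cover weeks 0–4 after an injection, and the Day 1 baseline is 0. The 4-week change is 0.875 − 0 = 0.875 in every session under every curve, as it should be for an identical true course.

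**Step 6. Day 1 DFSS-I.** Under the protocol wording, Day 1 looks back to screening, 1–21 days earlier. Under the SAP it looks back 28 days. The difference is 28 − 21 = 7 to 28 − 1 = 27 days, all before any study injection.

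**The case against.** Several points on the other side stand.

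- **Objective.** A reader might infer that comparing sessions is itself the secondary objective. It is not. Protocol 8.2 and SAP 1.1 ask for the magnitude of response at intervals after treatment, and SAP 2.9.1 analyses each session on its own. The risk lies in how the tables are read, not in a planned test.
- **13-week change.** A reader might infer that it is pulled toward benefit throughout Sessions 2–4. In Sessions 3 and 4 both ends have a 9-week look-back, so recall length cancels. Unequal recall affects mainly Session 2 (5 against 9 weeks). What remains is that the raw 13-week scores in Sessions 2–4 cover a longer period than in Session 1.
- **A single percentage.** Suppose DFSS-I is 4 at 4 weeks and rises linearly to 6 at 13 weeks. A 4-week recall then averages 5.56 and a 9-week recall 5.00, so the next change is −1.56 or −1.00, 36% smaller. That figure depends on one assumed curve: it becomes 22% if benefit ends at week 8 and 54% if peak holds to week 8. It also uses a 4-week recall that no baseline in Sessions 2–4 has.
- **Recall length as the only cause.** In the same example the true change is −2, so a 4-week recall still shrinks it by 22% (0.44/2). Any look-back at a later session's baseline covers treated weeks; the baseline reset each session also contributes.
- **Return to baseline.** Reinjection waits until the investigator judges that baseline status has returned (Protocol 10). This bears on how much benefit is left, but it describes the subject at the visit, not the preceding weeks.
- **DIS wording.** If subjects answer by current status, the DIS effect could differ. The rating forms are not in the text reviewed, so this cannot be settled here. DFSS-I has no such competing instruction.

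**Conclusion.** The point holds for DFSS-I and for DIS as far as its period wording governs. The unequal look-backs and the overlap of the Session 2–4 baselines with post-injection weeks follow directly from the recall rule and the schedule. If benefit persists in those weeks, the 4-week change from pre-injection is understated in Sessions 2–4, most in Sessions 3–4.

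The size is an assumption because the documents give no time course: 22–72% of peak benefit in the Session 3–4 baselines and 0–50% in the Session 2 baseline, across three curves and with raters averaging over the recall period. The case is firmer for Weeks 26 and 39, whose recall starts at week 4 after injection, than for Week 13, whose recall starts at week 8.

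The documents do not support reading this as a flaw in a planned cross-session comparison or as a bias in every 13-week change. USFR, diary DFSS-S and the primary safety objective are not affected. The Day 1 DFSS-I mismatch is a separate, smaller inconsistency.

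**What to change.** 1. In SAP 4.4 add, for DFSS-I and DIS, change from Day 1 at Weeks 4, 17, 30 and 43, and use it for any statement about response across sessions. It uses data the schedule already collects.
2. State that this comparison is conditional on subjects who remain, because Protocol 12.3 allows withdrawal for lack or loss of effectiveness.
3. Footnote the tables: 13-week scores in Session 1 and in Sessions 2–4 cover different periods.
4. Reconcile the Day 1 DFSS-I look-back between Protocol 15.4 and SAP 2.6.1, and the two DIS references within Protocol 15.5 (repeated in SAP 2.6.1), and state which one the collected ratings followed.

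The cost is one extra table column, a footnote and the reconciling text. Changing the instruction to a 4-week look-back at every visit is not recommended. It would leave the first 5 weeks of each 9-week interval unrated by these scales and would still cover treated weeks. It also comes too late for a SAP dated July 2018 whose section 3.4 already reports how the populations differ.
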